The questionnaires to assess patients' pharyngeal ventilatory perceptual potential/the quality of spontaneous nasopharyngeal perception during ventilation are administered when patients come to the consultation to request the results of the pharyngeal ventilatory perceptual analysis. The examiners are blinded, unaware of the results. Patients are randomly assigned according to their order of arrival. The first questionnaire consists of 7 items selected to aggravate or facilitate upper airways permeability (supine position, modified state of consciousness with muscle relaxation, tongue posture, cephalic flexion, cephalic extension, mandibular protraction, nostrils aperture). This first questionnaire try to evaluate if all subjects are able to feel aggravating or facilitating factors by on/off answers. The second questionnaire consists of 18 items related to upper airway collapsibility. Each item concerns the aggravating or facilitating factors perceived by the patient or the therapist with clinical maneuvers, factors known to be unfavourable to the permeability of the upper airways (snoring, oral ventilation, tonsils, dento-skeletal class, etc.), as well as two questionnaires used in the sleep laboratory of the André Renard clinic (Epworth Sleepiness Scale and FFF questionnaire).

[figure not shown]
For each of these items, the patient's or practitioner's response will be noted.

Performing the examination:

- Sensory-motor awareness of nasal and pharyngeal breathing (patient in a seated position): explain to the patient what to observe and feel and where (soft palate, tonsils, vibration during snoring, etc.)
- Read the questionnaire to the patient: it must be understood
- Ask the patient to answer each item and record the response.

The examination lasts approximately 20 minutes.

This examination requires patient involvement but carries no risks or side effects.

STATISTICAL ANALYSIS PLAN

(translation of the Statistical analysis report download in SAP section from an independent Biostatistician: [name], MyStat.be)

Software used for analysis: R version 4.4.1(R Core Team (2024). R: A language and environment for statistical computing. R Foundation for Statistical Computing, Vienna, Austria. URL <https://www.R-project.org/>) and Microsoft Excel for manipulating and preparing the data tables. data files used and appended: d1_final.csv, d2_final.csv

1 - d1_final.csv: sensitivity parameters taken from 112 patients

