2 - d2_final.csv: parameters taken from 101 patients (excluding CHR patients considered normal after polysomnography)

Discrete variables for classification into groups :

- STATUS3: 2 categories: healthy patients (= non-CHR control patients and normal CHR patients) and pathological patients (= CHR patients affected to varying degrees)
- STATUS4: 4 categories: control patients (= non CHR), normal patients (= CHR N), mild symptom patients (= CHR SL), moderate symptom patients (= CHR SM) and severe symptom patients (= CHR SS).

A. Descriptive statistics (based on file n°1 - sensitivity)

B. Descriptive statistics (based on file n° 2 - predictive score)

C. Normality tests for intermediate and final scores

- Parameter ST1 (SubTotal1) = aggravating parameters

Shapiro-Wilk normality test

- Parameter ST2 (SubTotal2) = facilitating parameters

Shapiro-Wilk normality test

- Parameter ST1+ST2 (SubTotal1+ SubTotal2) = subjective sensitivity of patients

Shapiro-Wilk normality test

- Parameter ISF (Intermediate Final Score) = subjective sensitivity of patients and practitioner

Shapiro-Wilk normality test

- Parameter TFS (Total Final Score) = subjective sensitivity of patients and practitioner + valuable factors

Shapiro-Wilk normality test

D. Spearman correlation tests between final scores and certain variables

E. Non-parametric tests on patient sensitivity :

Given the non-normal distribution of the various variables other than IFS and TFS, non-parametric tests (based on the median of the data) were applied to analyse the differences between the groups (according to the STATUS3 and STATUS4 classification criteria). To analyse any differences in sensitivity between patient groups, Kruskal-Wallis tests were applied. In this type of analysis, having a p-value greater than 1% and ideally greater than 5% would indicate the absence of differences between groups.

Then, to see if the median of a particular group is different from 0 (= no sensitivity: not feeling the differences in airflow induced by the different tests given by the operator), Wilcoxon tests were performed on each group of data. If the p-value is small (less than 5%, ideally less than 1%), the null hypothesis that the score is identical to 0 is rejected. In this case, it means that the patients in the test group feel the differences in airflow depending on their position. This is the case for all the patient groups tested on ST1, ST2 and ST1+ST2.

[figure not shown]

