F. Parametric tests on the prediction of patients' pathological status (SFI and SFT scores):

For these analyses, as the IFS and TFS scores follow a normal distribution, ANOVAs (analyses of variance) were performed. For discrete variables with more than 2 levels of value (STATUS4), a post-hoc 2-to-2 comparison analysis was performed (Tukey) to see which level of the variable differed from one another. Significant values are highlighted in bold red.

[figure not shown]
G. Determination of cut-off values for IFS and TFS:

[figure not shown]
The Cutoff_final txt file includes the various sensitivity and specificity calculations as well as the Youden index in order to determine the best cut-off value (largest Youden). The ROC curves allow the values in the file to be appreciated graphically.

Upper rhino-oro-pharyngeal airway permeability - Subjective neuro-sensory evaluation

Assessment of oro-pharyngeal sensitivity				
Date :	Name:			age:
Tests	Items			Score 1 0
	Aggravation or facilitation felt = 1 No aggravation or no facilitation felt = 0			
Aggravation maneuver	1	Supine position		
Aggravation maneuver	2	Modified state of consciousness (overall relaxation)		
Aggravation maneuver	3	Cephalic Flexion		
Aggravation or Facilitation maneuver	4	Upper-anterior tongue to lower tongue (= aggravation) or lower tongue to upper-anterior tongue (= facilitation)		
Facilitation maneuver	5	Cephalic Extension		
Facilitation maneuver	6	Mandibular protrusion		
Facilitation maneuver	7	Nostrils aperture		
Total Score				... / 7
Comments :				
www.osteovox.be				

Upper rhino-oro-pharyngeal airway permeability - Subjective neuro-sensory evaluation						
Date :	Name :			age: IMC:		
Tests	Items			Scores		
	0	0,5	1	2		
Aggravation maneuver	1	Supine position: aggravation=1 / no aggravation= 0				
Aggravation maneuver	2	Modified state of consciousness (overall relaxation) aggravation=1 / no aggravation= 0				

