Aggravation maneuver	3	Cephalic flexion: aggravation at the start of flexion ($\leq 6^\circ$)=2 / in the middle of flexion ($7\text{--}>10^\circ$)=1 / at the end of flexion ($\geq 11^\circ$)=0				
Facilitation maneuver	4	Cephalic extension: facilitation from the start of extension ($\leq 6^\circ$)=2 / in the middle of extension ($7\text{--}>10^\circ$)=1 / at the end of extension ($\geq 11^\circ$)=0				
Facilitation maneuver	5	Measurement of range: amplitude between cephalic flexion and extension: reduced ($\leq 12^\circ$)=2 / medium ($13\text{--}>20^\circ$)=1 / large ($\geq 21^\circ$)=0				
Facilitation maneuver	6	Mandibular advancement: Physiological=2 / Tooth butt =1 / Anterior crossing=0.5 / no facilitation= 0				
Therapist observation	7	Therapist palpation of the contraction of the buccal floor on inspiration at rest yes=2 / no=0				
Therapist observation	8	Sound perception of ventilation by the therapist: yes=1 / no=0				
Intermediate Final Score (IFS): low risk of OSA ≤ 7.5 / risk of OSA ≥ 8				... / 13		
Aggravated situation	9	Low lingual posture in supine position : yes=2 / no=0				
Subjective perception of nasal permeability	10	Do you regularly have difficulty breathing through your nose? yes=1 / no= 0				
Subjective perception of snoring	11	Do you snore at night? yes=1 / no=0				
Subjective perception of daytime ventilation patterns	12	During the day, you breathe mainly: through the mouth=1 / mixed nose-mouth=0,5 / through the nose =0				

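### The predictive-score file omits CHR patients with normal polysomnography, so the cut-offs, if derived from it, have no specificity in non-cases described as polysomnography-verified

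*Combined protocol and SAP*

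**What the plan says.** The SAP opens with two data files. The first is "d1_final.csv: sensitivity parameters taken from 112 patients". The second, d2_final.csv, holds "parameters taken from 101 patients (excluding CHR patients considered normal after polysomnography".

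Two grouping variables follow. STATUS3 has a healthy class, "healthy patients (= non-CHR control patients and normal CHR patients", and a diseased class, "pathological patients (= CHR patients affected to varying degrees". STATUS4 begins "STATUS4: 4 categories: control patients (= non CHR), normal patients (= CHR N" and goes on to mild, moderate and severe CHR groups. It announces four levels and lists five.

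Section B is headed "Descriptive statistics (based on file n° 2 - predictive score". Section F compares IFS and TFS between status groups, and section G derives cut-offs for both by the largest Youden index: "The Cutoff_final txt file includes the various sensitivity and specificity calculations". Neither F nor G names its data file in the text, and their figures and the cut-off file are not shown.

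The second questionnaire prints working thresholds. For the IFS it gives "low risk of OSA ≤ 7.5 / risk of OSA ≥ 8", and for the final total (FTS on the form, TFS in the SAP) low risk up to 10 and high risk from 11. The study-group and control-group paragraphs give 41 patients with OSA (9 mild, 18 moderate, 14 severe) and 60 controls classed as free of OSA from Epworth, Berlin, Pichot and FFF. No polysomnography is described for the controls.

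**The concern.** The only people the text describes as normal on polysomnography are the ones taken out of the predictive-score file. What remains sets patients from one label (CHR, all diseased) against people from another (non-CHR, all healthy). Any difference between the two sources, in referral, sex, age or weight, is then indistinguishable from a difference due to OSA.

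This matters because the protocol asks whether the felt sensations can add to screening, and the form prints cut-offs ready for use. A case-control contrast can show that the groups differ. It does not show how often the cut-off would wrongly flag someone who is investigated and proves normal. That figure would have no denominator in d2.

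**Working it through.** **Reproducing the file size.** Cases: 9 + 18 + 14 = 41. Cases plus controls: 41 + 60 = 101, the stated size of d2. No CHR normals remain in it. The difference between the files is 112 − 101 = 11. That these 11 are the CHR normals is inferred, and holds only if nothing else separates the files.

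**Status by label in d2**, from the STATUS3 and STATUS4 definitions:

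| | Cases | Non-cases |
|---|---|---|
| CHR | 41 | 0 |
| non-CHR | 0 | 60 |

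The two variables coincide. CHR is not defined in the text, so reading it as patient source is an assumption.

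**Case mix.** Men: 28/41 = 68% versus 20/60 = 33%. Mean age: 49.30 versus 41.76, a gap of 7.54 years. Mean BMI: 30.70 versus 22.78, a gap of 7.92 kg/m².

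**Overlap of control selection and score.** IFS, items 1–8: 1+1+2+2+2+2+2+1 = 13, with no Epworth or FFF. Items 9–18 add 2+1+1+1+2+1+1+1+2+1 = 13, giving 26 for the FTS. Epworth (2) and FFF (1) contribute 3/26 = 11.5% of the FTS maximum and nothing to the IFS.

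**Precision obtainable in 11 verified normals.** The documents give no scores for them, so these are ranges over assumed counts. The exact 95% (Clopper-Pearson) limits for x of n are the 2.5% quantile of Beta(x, n−x+1) and the 97.5% quantile of Beta(x+1, n−x); at x = n the upper limit is 1.

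| Test-negative | Specificity | 95% CI |
|---|---|---|
| 6/11 | 0.545 | 0.234–0.833 |
| 8/11 | 0.727 | 0.390–0.940 |
| 10/11 | 0.909 | 0.587–0.998 |
| 11/11 | 1.000 | 0.715–1.000 |

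**Pooling with the controls.** Assume 54/60 controls are negative. Pooled specificity is (54 + x)/71:
- x = 0: 0.761
- x = 8: 0.873
- x = 10: 0.901
- x = 11: 0.915

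Since 60/71 = 85% of the pool stays unverified, pooling does not settle the question.

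**A bias in the other direction.** Suppose a fraction p of controls has undiagnosed OSA, with true specificity 0.90 and sensitivity 0.80 (both assumed). Apparent specificity = (1 − p) × 0.90 + p × (1 − 0.80):
- p = 0.05: 0.865
- p = 0.10: 0.830
- p = 0.20: 0.760

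Case mix and, for the FTS, questionnaire overlap could raise apparent specificity. Undiagnosed OSA among controls could lower it. The documents do not allow the net effect to be signed.

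**The case against.** The protocol's stated comparator is a group free of sleep disorders, and leaving investigated patients out of the score file is compatible with that. The case-mix gap and the Epworth/FFF overlap come from how the controls were chosen, not from the exclusion, and restoring the CHR normals would leave the 60 controls unverified. About 11 patients give a very wide interval, and their 18-item scores may not exist, since d1 is described only as sensitivity parameters. All of this stands. It limits the benefit of the reanalysis, but it does not supply a specificity in verified normals.

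Cut-off selection also limits what can be compared. If the cut-off was chosen by maximum Youden in the same 41 + 60, specificity in the 60 is in-sample and an exact interval around it ignores the selection. The excluded patients would be out-of-sample. A lower figure in them could reflect cut-off optimism as well as patient source, so a formal test between the two would mislead.

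A reader might infer that F and G certainly used d2, that no control had polysomnography, or that no reason for the exclusion was ever given. The text supports none of these as fact. The F and G output is not shown, the control paragraph is merely silent on polysomnography, and the content of the flowchart the document mentions is not visible and may state the reason.

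**Conclusion.** The point holds in conditional form. It is explicit that d2 drops CHR patients normal on polysomnography whom STATUS3 calls healthy, and the counts confirm that 41 + 60 fills the file. If F and G use d2, as section B's label and the matching counts suggest, the specificity and Youden cut-offs for IFS and FTS include 0 non-cases described as polysomnography-verified and cannot separate OSA from CHR source.

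It is tempting to conclude that the reported specificity is too high. The documents do not support that: plausible biases run both ways, and neither direction nor size can be computed. The group comparisons can stand as comparisons; what needs limiting is the accuracy claim.

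This should be fixed, with medium confidence. It rests on three readings: that F and G use d2, that CHR denotes patient source, and, for the number 11 only, that the CHR normals are the sole difference between the files. The STATUS4 count is a minor labelling slip. Its CHR N level is not itself an error, because the variable may serve both files, and four levels is right for d2.

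**What to change.** 1. Check whether the 18-item scores exist for the excluded CHR normals. If they do, report specificity at the fixed IFS and FTS cut-offs separately for them, with an exact interval, as a descriptive result. State that the figure in the 60 controls is in-sample, because the cut-off was chosen by maximum Youden in the same data. Do not test one figure against the other. Keep any 41-versus-71 rerun as a sensitivity analysis only.
2. If the scores do not exist, say so and limit the accuracy claim to OSA patients versus questionnaire-screened non-CHR controls.
3. In either case, state that no polysomnography is described for the controls, and that Epworth and FFF serve both control selection and the FTS, but not the IFS.
4. State the reason for the exclusion and the file behind F and G, unless the flowchart or output not shown here already does so.
5. Correct the STATUS4 count and say which levels apply in d2.

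The cost is one rerun at fixed cut-offs if the scores exist, otherwise a few sentences. The downside is an imprecise estimate and an accuracy claim that may look less favourable.

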- Altered state of consciousness (first sleep stage)
- Mouth breathing and loss of lingual-palatal and labial-labial contact
- Passive craniocervical flexion

Facilitating parameters:

- Cephalocervical extension
- Mandibular advancement
- Tongue protraction
- Efficient nasal ventilation

These considerations allow us to establish an examination protocol to attempt to answer the following questions:

- Can the subject consciously perceive variations in airflow/or intraluminal pressure in the upper airways caused by the various aggravating and facilitating parameters?
- Can the sensations of ventilatory flow/intraluminal pressure felt by the subject constitute a complementary tool for screening for obstructive sleep disorders?

The goal of the clinical examination is to cause instability of the oropharyngeal mechanics. This instability can cause a modification of the pharyngeal lumen and a modification of the resistance of the VAS to the pressure linked to the ventilatory flow. These will lead to a modification of the inspiratory pressure gradient and stimulate the mechanoreceptors located in the VAS. The responses to a questionnaire by subjects who present sleep disorders exposed to these variations in resistance (aggravating or facilitating) on their subjective feeling allows the establishment of a perception scale which, compared to a control group without sleep disorders, will determine if the sensitivity of the inputs is comparable between the groups and if a tool for screening sensory inputs is possible.

Protocol:

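### Sections F and G analyse IFS and TFS only, so the visible plan does not show what felt sensation adds to the ordinary screening items, which is what question 2 asks

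*Combined protocol and SAP*

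**What the plan says.** Among the questions that the protocol sets itself is: "Can the sensations of ventilatory flow/intraluminal pressure felt by the subject constitute a complementary tool for screening for obstructive sleep disorders".

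SAP Section C defines three nested scores:

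- "Parameter ST1+ST2 (SubTotal1+ SubTotal2) = subjective sensitivity of patients"
- "Parameter ISF (Intermediate Final Score) = subjective sensitivity of patients and practitioner" (also written IFS)
- "Parameter TFS (Total Final Score) = subjective sensitivity of patients and practitioner + valuable factors" (called FTS on the form)

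On the 18-item form, IFS is items 1-8, out of 13. It is not made up only of what the patient feels. Item 5 is a measured range of movement, item 8 is what the therapist hears, and item 7 reads "Therapist palpation of the contraction of the buccal floor on inspiration at rest yes=2 / no=0". TFS then adds items 9-18, for a total out of 26. These run from "Low lingual posture in supine position : yes=2 / no=0" and "Do you regularly have difficulty breathing through your nose? yes=1 / no= 0" through snoring, mouth breathing, dento-skeletal class, tonsils and Mallampati to Epworth and FFF. The protocol text describes several of them as already known to be unfavourable, and Epworth and FFF as questionnaires in use in the sleep laboratory.

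Section E tests ST1, ST2 and ST1+ST2 between groups and against zero. Section F runs ANOVAs on IFS and TFS. The next heading is "G. Determination of cut-off values for IFS and TFS", with ROC curves and the Youden index. The visible text names no score or ROC for items 9-18 alone, no model holding sensation and the other items together, and no paired comparison of ROC curves.

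**The concern.** To call a tool complementary is to say something about a step: start from the items that a clinician would ask about anyway, add the sensation items, and see whether discrimination improves. The ordinary items are already on the form as items 9-18, yet the visible plan does not analyse them on their own. Setting the IFS ROC beside the TFS ROC measures the opposite step, what items 9-18 add to IFS.

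The two halves are added with equal maximum weight. A weak IFS can therefore lower the discrimination of the sum below that of items 9-18 alone, while the sum still looks good. The study title ties predictive value to the subjective feeling of airflow, so a good TFS curve could easily be credited to sensation without evidence on that step.

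**Working it through.** **1. Reproduce the form's totals** (item maxima from the 18-item form).

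- Items 1-8: 1+1+2+2+2+2+2+1 = 13, matching the printed 13.
- Items 9-18: 2+1+1+1+2+1+1+1+2+1 = 13, so TFS = 26, matching the printed 26.
- Items 9-16, without Epworth (2) and FFF (1): 13 - 3 = 10.
- Patient-felt manoeuvre items 1, 2, 3, 4 and 6: 1+1+2+2+2 = 8. The rest of IFS is item 5 (2), item 7 (2) and item 8 (1), which is 5 of 13.

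**2. Model.** Let P = IFS and R = items 9-18, both normal within group, with standardised group differences dP and dR, SD ratio k = SD(P)/SD(R) and within-group correlation rho. Then

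- AUC(P) = Phi(dP/sqrt(2)) and AUC(R) = Phi(dR/sqrt(2))
- AUC(TFS) = Phi((k·dP + dR)/sqrt(2(k² + 1 + 2k·rho)))

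All AUCs, k and rho below are assumptions; the documents state none.

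**3. TFS alone.** Hold AUC(TFS) at 0.85 with k = 1 and rho = 0. If IFS has AUC 0.80, items 9-18 alone have 0.734 and IFS adds 0.116. If IFS has 0.50, they have 0.929 and IFS costs 0.079. The planned IFS ROC would tell these two cases apart, so the test that matters is the next one.

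**4. Both planned ROCs known.** Fix AUC(IFS) = 0.70, so dP = 0.5244 × 1.4142 = 0.7416, and AUC(TFS) = 0.85, with normal quantile 1.0364. Solve dR = 1.0364·sqrt(2(k² + 1 + 2k·rho)) - k·0.7416.

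- k = 0.7, rho = -0.2: dR = 1.0364 × sqrt(2.42) - 0.519 = 1.093, so AUC(R) = Phi(0.773) = 0.780.
- k = 1.4, rho = 0.5: dR = 1.0364 × sqrt(8.72) - 1.038 = 2.022, so AUC(R) = Phi(1.430) = 0.924.

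AUC of items 9-18 alone, with what IFS adds in brackets (0.85 minus that AUC):

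| k | rho -0.2 | rho 0 | rho 0.2 | rho 0.3 | rho 0.5 |
|---|---|---|---|---|---|
| 0.7 | 0.780 (+0.070) | 0.815 (+0.035) | 0.844 (+0.006) | 0.857 (-0.007) | 0.878 (-0.028) |
| 1.0 | 0.784 (+0.066) | 0.827 (+0.023) | 0.860 (-0.010) | 0.874 (-0.024) | 0.898 (-0.048) |
| 1.4 | 0.808 (+0.042) | 0.853 (-0.003) | 0.887 (-0.037) | 0.901 (-0.051) | 0.924 (-0.074) |

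The sign changes within modest values: at k = 1 it turns between rho 0 and rho 0.2.

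**5. Would group means and SDs of IFS and TFS settle it?** No. They give the mean gap in R by subtraction, but Var(TFS) = Var(P) + Var(R) + 2·rho·SD(P)·SD(R) is one equation in two unknowns, SD(R) and rho.

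**The case against.** **IFS is analysed separately.** It has its own ANOVA, ROC and cut-off, and ST1+ST2 has its own group tests. A reader might infer that the plan buries sensation inside TFS and never looks at it separately; the documents do not support that. Under equal SDs and independence the two planned AUCs even determine the third: with 0.70 and 0.85, items 9-18 alone have 0.827. This stands. The ambiguity comes from the unknown SD ratio and correlation, and the described analyses do not report these for items 9-18.

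**Complementary may be meant loosely.** Soon after the questions, the protocol states a more modest aim, whether a sensory screening tool is possible at all, and the stand-alone performance of IFS speaks to that. This stands in part. The gap concerns the stronger word in question 2, which stand-alone discrimination does not establish.

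**The output is not visible.** The figures in Sections E to G and the cut-off file are missing from the text, and Section D correlates final scores with variables that it does not name. This stands, so the point is limited to what the text names.

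**The split of items is not clean.** The form labels items 10-13 as subjective perception. They are self-reported symptoms and habits, though, not sensations under a manoeuvre. Item 5 is less certain. Its cut-points of 12 and 20 degrees are twice the 6 and 10 degrees of items 3 and 4, so it may be built from the felt angles. If so, 3 rather than 5 IFS points are clearly not sensation. The gap is the same either way.

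**Conclusion.** The point holds, in limited form. The visible plan shows how well IFS and TFS discriminate and what items 9-18 add to IFS. It does not show what felt sensation adds to the ordinary items, and the two planned ROC curves do not determine even the direction. In the worked example the added value runs from a gain of 0.070 to a loss of 0.074 in AUC. That range rests on a binormal model, assumed AUCs of 0.70 and 0.85, SD ratios of 0.7-1.4 and correlations of -0.2 to 0.5. Other values would move the limits.

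A reader might go further and infer that sensation adds nothing, that TFS discriminates only through snoring-type items, or that items 9-18 suffice. The documents contain no AUCs and support none of these. The analyses of IFS and TFS remain valid for what they measure. The change should be made because, without it, question 2 has no analysis directed at its key word.

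**What to change.** Add to Section G, on the 101 patients in d2_final.csv (41 cases, 60 controls), labelled post hoc because the analysis text already reports results:

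1. The ROC and AUC of items 9-16 (0-10) as the main comparator, with items 9-18 as a sensitivity analysis. Controls were classed as free of OSA using Epworth and FFF among other scales, so items 17-18 can flatter the comparator.
2. A logistic model of STATUS3 on that comparator, with and without the patient-felt score (items 1, 2, 3, 4 and 6, 0-8), with the likelihood-ratio test and the sign of the coefficient. Repeat with the full IFS.
3. The paired AUC difference, with 95% CI by DeLong or bootstrap, between the comparator and the comparator plus the patient-felt score, and likewise plus IFS. Use the unweighted sums, so that no coefficient is fitted and judged on the same patients.

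Call sensation complementary only if the interval for added value excludes no gain. Otherwise state that added value was not shown. Do not conclude that the ordinary items suffice: with 41 cases a null result cannot carry that.

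The cost is a few lines of R on existing data, provided that the items are stored separately. The interval will be wide, and the claim may become less favourable.

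### SAP section E reads a non-significant Kruskal-Wallis test as absence of difference and a Wilcoxon rejection of 0 as proof that a group feels the manoeuvres; neither conclusion follows from its test

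*Combined protocol and SAP*

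**What the plan says.** The introductory part of the protocol sets a comparability aim: comparison with a control group "will determine if the sensitivity of the inputs is comparable between the groups". The Protocol section gives the purpose of the seven-item form: "This first questionnaire try to evaluate if all subjects are able to feel aggravating or facilitating factors by on/off answers".

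SAP section E serves these aims with two rules.

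- **Between groups.** Kruskal-Wallis tests across the STATUS3 and STATUS4 classes, with the reading that "having a p-value greater than 1% and ideally greater than 5% would indicate the absence of differences between groups".
- **Within each group.** Wilcoxon tests "to see if the median of a particular group is different from 0 (= no sensitivity: not feeling the differences in airflow" produced by the manoeuvres). The rule is: "If the p-value is small (less than 5%, ideally less than 1%), the null hypothesis that the score is identical to 0 is rejected". Rejection is interpreted thus: "it means that the patients in the test group feel the differences in airflow depending on their position". The outcome is given as: "This is the case for all the patient groups tested on ST1, ST2 and ST1+ST2".

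The visible text gives no equivalence margin, confidence interval or power for either rule. It does not state how the Wilcoxon test treats zeros. The accompanying results are in a figure that is not shown.

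**The concern.** **Kruskal-Wallis.** Failure to reject is not evidence of equality, least of all with groups of 9 to 18. Allowing p between 1% and 5% to count as absence makes the claim easier still: p = 0.02 would pass. The protocol's own background suggests that receptor sensitivity may be diminished in severe OSA, so a deficit confined to the 14 severe patients is a plausible alternative, and the test is weak there.

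**Wilcoxon against 0.** Items on both forms score 0 or more, so every non-zero value is positive. With zeros dropped, the p-value depends on how many subjects are non-zero and how tied their scores are, not on what share of the group they form. A small minority can produce rejection in a large group.

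These are the only tests the visible text offers for the question whether subjects perceive the changes, and for comparability.

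**Working it through.** **Inputs.** Controls 60; OSA patients 41 = 9 mild + 18 moderate + 14 severe (sample description after the questionnaires). The sensitivity file holds "sensitivity parameters taken from 112 patients" and the second file 101, from which normal CHR patients are excluded. Hence normal CHR = 112 − 101 = 11 (inferred), and 60 + 41 = 101 agrees. STATUS3 is then 60 + 11 = 71 healthy v 41 pathological. STATUS4 is announced as four categories but names five; the five are used here. The plan gives no design figure for section E to reproduce.

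**1. Kruskal-Wallis** (simulated, normal scores; effect sizes are assumptions)

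| Test | Who is lower | Deficit | p < 5% | p < 1% |
|---|---|---|---|---|
| 60/11/9/18/14 | severe only | 0.5 SD | 20–21% | 6–7% |
| 71 v 41 | severe only | 0.5 SD | 12–14% | 3–4% |
| 71 v 41 | severe only | 0.8 SD | 23–24% | 8–9% |
| 71 v 41 | all 41 | 0.5 SD | about 70% | about 45% |
| 71 v 41 | all 41 | 0.8 SD | 97–98% | 91% |

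Pooling dilutes a severe-only deficit: 0.5 × 14/41 = 0.17 SD averaged over the pathological group, against a standard error of √(1/71 + 1/41) = 0.196 SD.

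**2. Wilcoxon against 0** (assumed: R's default when zeros are present, i.e. zeros dropped, normal approximation with continuity and tie correction)

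With k non-zero values, all positive:

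z = [k(k+1)/4 − 0.5] / √[k(k+1)(2k+1)/24 − Σ(t³ − t)/48], where t are the sizes of the tied sets.

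- k = 5, all equal: 7/√11.25 = 2.09, p = 0.037. Four equal plus one: 7/√12.5 = 1.98, p = 0.048. All distinct: 7/√13.75 = 1.89, p = 0.059.
- k = 6, all equal: 10/√18.375 = 2.33, p = 0.020. All distinct: 10/√22.75 = 2.10, p = 0.036. Every pattern rejects at 5%. The exact test agrees: 2/2⁶ = 0.031.
- k = 8, all equal: 17.5/√40.5 = 2.75, p = 0.006. Seven equal plus one: 17.5/√44 = 2.64, p = 0.008. Other patterns do not reach 1%.
- k = 9, all distinct (the least favourable pattern): 22/√71.25 = 2.61, p = 0.0092. Every pattern rejects at 1%.

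Group size n does not enter. A sample median of 0 allows at most n/2 − 1 non-zero values if n is even and (n − 1)/2 if odd:

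| Group | n | Most non-zero with median 0 | Rejection possible at 5%? | At 1%? |
|---|---|---|---|---|
| Control | 60 | 29 | yes | yes |
| Healthy | 71 | 35 | yes | yes |
| Pathological | 41 | 20 | yes | yes |
| Moderate | 18 | 8 | yes | only with exactly 8, at least 7 equal |
| Severe | 14 | 6 | yes | no |
| Normal CHR | 11 | 5 | only with exactly 5, at least 4 equal | no |
| Mild | 9 | 4 | no (4 equal: p = 0.072) | no |

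Six subjects are 10% of the controls and 15% of the pathological group.

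**The case against.** **The reported result is probably not an artefact.** Section E reports rejection in every group. If all five STATUS4 groups were tested, very low response rates are unlikely: with three independent on/off items and 10% answering yes to each, all five groups reject together on one score in only about 0.2% of simulated runs. This stands. A reader might infer that the subjects do not feel the manoeuvres; the documents do not support that. Illustrations for a single group also depend heavily on an unknown: with 5% yes per item, three items and n = 60, rejection occurs in about 95% of runs if items are independent but about 49% if they correlate at 0.5.

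**The Wilcoxon problem is uneven.** This also stands. A reader might take it that any group, however small, could be declared sensitive with a median of 0. That is impossible in the mild group, a narrow case in normal CHR at 5% and in moderate at 1%, and impossible in severe at 1%.

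**Large differences would be found.** True if the whole pathological group is shifted by 0.8 SD; not true of a deficit confined to severe patients.

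**Zero handling is assumed.** Correct, but keeping zeros in the ranking (Pratt) lowers the number of non-zero subjects needed at 5% to four or five.

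**Section A may already tabulate proportions.** Possibly; its output is not visible. Then only intervals and wording are missing.

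**Conclusion.** Both decision rules are wrong as written. A Kruskal-Wallis p above 1% or 5% does not show comparability: a 0.5 SD deficit confined to the severe group would be read as absence in about 79–80% of five-group analyses at the 5% threshold and 93–94% at 1%. Rejecting 0 by Wilcoxon does not show that a group's patients feel the changes, still less that all subjects do. It is compatible with a sample median of 0 in the control, healthy and pathological groups at either level, and in moderate and severe at 5%.

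The power figures rest on assumed effect sizes and an inferred 11 normal CHR patients; the Wilcoxon counts rest on R's default. The finding concerns what the rules can show. With the result tables not visible, it cannot be said that the groups differ or that the reported sensitivity is false. Nor does it reach the IFS and TFS cut-offs in sections F and G, which do not use these tests.

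**What to change.** 1. **Define ST1 and ST2 first: which form, which items.** On the second form, items 1–6 sum to at most 1+1+2+2+2+2 = 10, and the two therapist items bring this to the 13 of the IFS, so ST1 and ST2 may be second-form sums. If so, a 0 need not mean that nothing was felt: flexion felt only at the end scores 0, and item 5 is a range measurement. The on/off illustration under the objection would then not apply.
2. **Between groups.** Say that no difference was shown and drop the 1% threshold for absence. Report each group-versus-control difference with a 95% CI (Welch for mean scores, or a difference in proportions). Claim comparability only against a justified margin. The SAP is presented as a translation of the analysis report, so a margin set after the data were seen must be labelled post hoc.
3. **Within groups.** Replace the Wilcoxon conclusion with the proportion feeling each manoeuvre, from the on/off items of the first questionnaire, and the proportion scoring above 0, with exact 95% CIs. State that the median is above 0 only if the lower limit for the latter exceeds 50%. The smallest counts that achieve this are 39/60 controls, 10/11 normal CHR, 8/9 mild, 14/18 moderate, 12/14 severe, 45/71 healthy and 28/41 pathological.

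**Cost.** Rewording and intervals from the existing files in R; no new data. The drawback is precision: 1.96 × √(1/n + 1/60) gives half-widths against controls of 0.70, 0.64, 0.58 and 0.53 SD for n = 9, 11, 14 and 18, and up to about 0.78 SD for n = 9 with Welch intervals. Comparability in the OSA subgroups will probably be inconclusive, and the report should say so.
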